9.2. Analyses Sets

9.3. Statistical Analyses

9.3.1. General Considerations

Statistical analysis of this study will be the responsibility of sponsor or its designee. A detailed SAP describing the statistical methodologies will be developed by the sponsor or its designee.

Handling of missing, unused, and spurious data are addressed prospectively in the overall statistical methods described in the protocol and in the SAP, where appropriate. Adjustments to the planned analyses are described in the final CSR.

Efficacy analyses will be conducted on the mITT population, unless otherwise specified. Safety analyses will be conducted on the safety population. Placebo participants will be pooled for

This study includes

- Period I screening period
- Period II CC double-blind, placebo-controlled treatment period
- Period III CC double-blind treatment period, and
- Period IV post-treatment follow-up.

Efficacy and safety data will be analyzed and summarized by these treatment periods if appropriate

Period II - double-blind, placebo-controlled treatment period
 Period III - double-blind treatment period.
 CCI
 CCI
 CCI

Baseline for the Treatment Period is defined as the last non-missing assessment on or prior to the date of the CC of study treatment. Any assessment collected after the CC is defined as post-baseline for the Treatment Period. Change from baseline will be calculated as the visit value of interest minus the baseline value. If a baseline value or the value at the visit is missing for a particular variable, then the change from baseline is defined as missing.

Summary statistics for continuous variables may include mean, standard deviation, median, and minimum and maximum values.

Categorical variables will be presented as counts and percentages. Variables will be analyzed in the original scale on which they are measured, unless otherwise specified.

The parametric approach will be employed by default for statistical analysis except when nonparametric analysis, such as by a rank-based method, is more fitting.

Additional exploratory analyses of the data will be conducted as deemed appropriate.

Dichotomous responder endpoints including the primary endpoint will be analyzed using a **CC**

The odd ratio and p-value based on odd ratio will be reported. CCI of mean difference will also be reported without being adjusted by covariates. Missing data will be imputed using the nonresponder imputation method.

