For analyses in Period 2, participants randomized to either Placebo subcutaneous (SC) Q4W to Peresolimab 400 mg SC Q4W or Placebo SC Q4W to Peresolimab 1000 mg SC Q4W will be combined as Placebo SC Q4W.

Dichotomous efficacy endpoints including the primary endpoint during Period 2 will be analyzed using a CCI

Period 2, an estimate of the treatment difference with corresponding Wald 95% confidence interval (CI), the odds ratio with corresponding Wald 95% CI and p-value will be presented. Each treatment group will be compared to Placebo SC Q4W.

Continuous efficacy endpoints, which are planned to be collected at >1 postbaseline timepoints during Period 2 according to the SoA, will be analyzed using mixed-effect model for repeated measures (MMRM) analysis. The MMRM model will include:

- treatment, stratification factors, baseline value, visit and treatment-by-visit interaction in the model as fixed factors, and
- participant as a random factor.

The least squares (LS) mean for each treatment group along with the estimate of the difference between each treatment group with Placebo SC Q4W, standard error (SE), p-value, and the 95% CIs will be reported at each visit along with p-values.

The covariance structure to model the within-participant errors will be unstructured. If the unstructured covariance matrix results in a lack of convergence, the heterogeneous Toeplitz covariance structure, followed by the CCI, will be used.

The CCI will be used to estimate the denominator degrees of freedom.

Type III sums of squares for the LS means will be used for the statistical comparison. The 95% CI will also be reported.

When continuous efficacy endpoints are analyzed using CCI , the model will include treatment group, stratification factors, and baseline value as covariates. Type III sums of squares for the LS means will be used for statistical comparison between each treatment group and Placebo SC Q4W. The LS mean difference, SE, p-value, and 95% CI, unless otherwise specified, will also be reported.

Dose response modeling will be performed on the primary, and other core efficacy endpoints, if deemed necessary, to assist in dose selection decisions. More details will be provided in Section 4.2.

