4.4.2.1.8. SDAI Remission and Low Disease Activity

SDAI remission and LDA at Week 12 for the peresolimab treatment group will be compared with placebo.

A logistic regression model will be used, as described in Section 4.1, to test the treatment difference of each peresolimab treatment group versus placebo. A composite strategy will be used to handle intercurrent events. Any missing data (for example, missing due to missing a visit) will be imputed using NRI.

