4.9. Changes to Protocol-Planned Analyses

There is no change to protocol-planned analyses.

5. Sample Size Determination

Approximately 420 participants CCI

- 100 mg of peresolimab Q4W
- 400 mg of peresolimab Q4W
- 1000 mg of peresolimab Q4W
- Placebo to 400 mg of peresolimab Q4W, or
- Placebo to 1000 mg of peresolimab Q4W.

CCI

- At Week 12, the 100 mg peresolimab treatment group will have a sample size of approximately 60 participants, and the 400 mg and 1000 mg peresolimab treatment groups will each have a sample size of approximately 120 participants.
- At Week 12, the placebo group will have a sample size of approximately 120 participants.

6. Supporting Documentation

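### Wald intervals are the stated method for every Week 12 binary endpoint, and if ACR70 or remission rates are only a few percent, the difference interval under-covers and the odds ratio can fail

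*SAP*

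**What the plan says.** SAP 4.1 sets one approach for all binary efficacy endpoints of the placebo-controlled period: "Dichotomous efficacy endpoints including the primary endpoint during Period 2 will be analyzed using a" method whose name is redacted. The visible text then asks for "an estimate of the treatment difference with corresponding Wald 95% confidence interval (CI" and adds that "the odds ratio with corresponding Wald 95% CI and p-value will be presented".

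Protocol 9.3.1 agrees: "The odd ratio and p-value based on odd ratio will be reported", and the interval "of mean difference will also be reported without being adjusted by covariates".

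The strict endpoints follow the same route. SAP 4.4.2.1.1 analyses ACR70 as ACR20 is analysed. SAP 4.4.2.1.6 to 4.4.2.1.9 do the same for the four remission endpoints; for SDAI, "A logistic regression model will be used, as described in Section 4.1". Table KDAF.4.2 applies this to each dose against placebo at Week 12, the designated secondary timepoint, and at the other Period 2 visits.

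On arm sizes, SAP Section 5 states that "the 100 mg peresolimab treatment group will have a sample size of approximately 60 participants". It puts each of the two higher doses at about 120, and pooled placebo also at about 120.

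The only small-number rule in view, in SAP 4.7.1, concerns subgroup size, not the number of responders.

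**The concern.** Wald methods rest on a normal approximation that weakens when an arm has few responders. ACR70 and remission are the most demanding binary endpoints in the plan. About 70% of participants are to have a history of inadequate response to biologic or targeted synthetic DMARDs (Protocol 1.1). Nonresponder imputation and the composite strategy can only lower the rates. Counts of a few responders, or none, in an arm of 60 are therefore plausible, although the documents do not state them.

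Two things would then go wrong, in opposite directions:

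- The difference interval would usually be too short and badly placed.
- The odds ratio would be conservative, and would have no finite estimate when one arm has no responders.

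A table could thus show a difference interval that excludes zero beside a p-value near 1. Without a stated fallback, the analyst would have to choose one after seeing the fit fail.

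**Working it through.** **Inputs from the documents.** Arm sizes are from SAP Section 5: 60 + 120 + 120 + 120 = 420, which reproduces the stated total. The difference interval is unadjusted (Protocol 9.3.1), so a two-sample binomial calculation fits it.

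**Assumed inputs.** The documents give no response rate for any endpoint, so a range is used. The one visible hint is the dose-response intercept prior in SAP 6.9.2 (mean −2, SD 1.2 on the logit scale): median 1/(1+e²) = 11.9%, and −2 ± 1.96 × 1.2 gives 1.3% to 58.7%. It is a prior for the dose-response model, not a planning rate for remission.

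**Formulas.** With x₁ responders of 60, x₂ of 120, a = x₁/60 and b = x₂/120:

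- Wald difference interval: a − b ± 1.96 √[a(1−a)/60 + b(1−b)/120].
- Coverage: the sum of Binomial(60, p₁) × Binomial(120, p₂) probabilities over all tables whose interval contains p₁ − p₂.
- Chance that at least one arm has no responders: 1 − [1 − (1−p₁)⁶⁰][1 − (1−p₂)¹²⁰]. At 2% each: 1 − (1 − 0.298)(1 − 0.089) = 36%.
- Wald odds ratio: the log odds ratio with SE √[1/x₁ + 1/(60−x₁) + 1/x₂ + 1/(120−x₂)], undefined if x₁ or x₂ is 0.

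**Results, 100 mg against placebo (60 v 120), exact enumeration:**

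| Assumed rates, 100 mg / placebo | Wald difference coverage | Newcombe coverage | Chance of an arm with no responders |
|---|---|---|---|
| 1% / 1% | 98.1% | 99.2% | 68% |
| 2% / 2% | 93.0% | 98.0% | 36% |
| 3% / 3% | 91.0% | 97.3% | 18% |
| 5% / 5% | 92.6% | 96.4% | 4.8% |
| 10% / 10% | 93.9% | 95.7% | 0.2% |
| 2% / 1% | 70.0% | 98.7% | 51% |
| 3% / 1% | 83.5% | 98.6% | 41% |
| 5% / 1% | 90.0% | 98.1% | 33% |
| 5% / 2% | 91.6% | 97.8% | 13% |
| 30% / 30% | 94.5% | 95.0% | 0% |

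The 70.0% has a simple cause. At 2%, the 100 mg arm has no responders with probability 0.98⁶⁰ = 29.8%, and every such interval lies below the true difference of 1 point. The misses are lopsided elsewhere too: at 3% / 3%, 8.1% of intervals lie below the true value and 0.8% above. Miettinen-Nurminen coverage over assumed rates of 1% to 10% is 94.6% to 96.3%.

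**Odds ratio, 60 v 120.** Where it can be computed, the Wald interval covers 96.5% to 99.9% at equal rates of 1% to 10%. The true size of a nominal 5% Wald test, counting tables with an empty arm as non-rejections, is 0.0002, 0.004, 0.012, 0.024 and 0.035 at 1%, 2%, 3%, 5% and 10%.

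**Example, 6/60 v 0/120.** The Wald difference interval is 0.10 ± 1.96 √(0.1 × 0.9/60), or 2.4% to 17.6%; Newcombe gives 3.8% to 20.1%. The logistic fit does not settle (SE about 2,200) and its Wald p is about 0.99. Fisher's p is 0.0012 and the likelihood-ratio p is 0.0002.

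**Larger arms, 120 v 120.** Wald difference coverage is 95.6% at 3% / 3% and 95.2% at 5% / 5%, but 89.9% at 2% / 1% and 91.7% at 5% / 1%. Placebo has no responders with probability 0.98¹²⁰ = 8.9% at 2% and 0.99¹²⁰ = 30% at 1%; all three odds ratios then fail together.

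The logistic calculations are unadjusted. Stratification factors could make separation more likely; that was not simulated.

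**The case against.** **The redaction.** The sentence naming the binary method is blacked out in both documents, and a sparse-data rule could sit there. This stands: its absence cannot be asserted. It does not undo the visible Wald prescription for the difference and the odds ratio.

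**The p-value is not called Wald.** This stands. The word is attached to the intervals; a Wald p-value is the natural reading, not a stated fact. A likelihood-ratio p-value would survive an empty arm, but the odds ratio and its Wald interval would not.

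**Rarity is an assumption.** This also stands. At 10% the loss is about one point of coverage, and an empty arm is very unlikely.

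**An empty arm often costs nothing.** Largely true under equal rates: the chance of an empty arm together with Fisher p < 0.05 is 1.1%, 0.9% and 0.8% at 2%, 3% and 5%. It grows with a real effect, to 5.2% at 5% / 2% and 8.4% at 10% / 2%.

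**Newcombe is also off nominal.** At 2% / 2% its 98.0% is further from 95% than Wald's 93.0%, though on the safe side. Miettinen-Nurminen is closer.

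**Stakes.** These are secondary endpoints in a phase 2b trial without multiplicity adjustment, so no formal success claim rests on them.

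**Conclusion.** The point holds in a conditional form. The stated Wald difference interval is a poor choice if Week 12 rates for ACR70 or remission are about 2% to 5%: coverage is then about 91% to 93% at equal rates, and as low as 70% at 2% against 1%. The Wald odds ratio is conservative at those rates and breaks down when an arm has no responders. All of this rests on assumed rates, an unadjusted calculation and the unpooled Wald formula.

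A reader might infer more than the documents support:

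- **That all the Wald results are too narrow.** Only the difference interval under-covers, and at 1% / 1% it over-covers.
- **That the primary analysis is compromised.** At assumed rates of 30/30, 50/30 and 55/35 percent, Wald difference coverage for 60 v 120 is 94.5% to 94.6%.
- **That the dose-response work inherits the problem.** SAP 4.2 uses Bayesian model averaging with posterior quantiles, not these intervals.
- **That only the 100 mg comparison is exposed.** An empty placebo arm breaks every odds ratio.

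It is worth correcting because the cost is small, but it concerns secondary results only.

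**What to change.** In SAP 4.1, replace the Wald interval for the difference with a Miettinen-Nurminen interval (Newcombe is acceptable) for the binary endpoints. Both can be computed with an empty arm.

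For the odds ratio and its p-value, name the test, and prespecify Firth-penalised logistic regression or an exact test when any compared arm has no or very few responders, with the threshold fixed as a number in advance. If the redacted text already has such a rule, pointing to it is enough for this part.

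The cost is SAP wording and standard software options. Difference intervals become somewhat wider at low rates. The penalised odds ratio stays conservative but is always finite: its interval covers 96.6% to 100% over the assumed rates of 1% to 10%. For 6/60 v 0/120, adding 0.5 to each cell gives 6.5 × 120.5 / (54.5 × 0.5) = 28.7, with SE of the log √(1/6.5 + 1/54.5 + 1/0.5 + 1/120.5) = 1.48 and an interval of about 1.6 to 519.

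SAP Version 3 was written for the final lock, after the primary one. If Week 12 tables already exist, add the score intervals and sparse-data results as labelled supplementary output.

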Treatment comparisons of continuous efficacy endpoints with multiple postbaseline timepoints will be analyzed using CCI will include

- treatment
- stratification factors
- baseline value
- visit, and treatment-by-visit interaction in the model as fixed factors, and
- participant as a random factor.

The covariance structure to model the within-participant errors will be unstructured. If the unstructured covariance matrix results in a lack of convergence, the heterogeneous Toeplitz covariance structure, followed by the CCI will be used.

The CC will be used to estimate the denominator degrees of freedom. Type III sums of squares for the LS means will be used for the statistical comparison. The 95% CI will also be reported. Missing data will be handled with the missing at random assumption. No additional imputation methods will be applied to the CC

Where appropriate, treatment comparisons of continuous efficacy endpoints will be analyzed using CCI modeled with treatment group, stratification factors, and baseline value as covariates. Type III sums of squares for the LS means will be used for statistical comparison between treatment groups. The LS mean difference, standard error, p-value, and otherwise specified, will also be reported. Missing data imputation method for the CCI model will the last observation carried forward.

Dose response modeling will be performed on the primary objective to assist in dose selection decisions. More details will be provided in the SAP.

Any change to the data analysis methods or imputation methods described in the protocol will require an amendment only if it changes a principal feature of the protocol. Any other change to the data analysis methods described in the protocol, and the justification for making the change, will be described in the SAP and the clinical study report. Additional exploratory analyses of the data may be conducted as deemed appropriate.

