2.1. Multiplicity Adjustment

Adjustment for multiple comparisons will not be employed in the analysis for this study.

3. Analysis Sets

Abbreviations: CDAI = Clinical Disease Activity Index; LDA = low disease activity; Q4W = every 4 weeks; Q12W = every 12 weeks; SC = subcutaneous.

Table KDAF.3.1. Treatment Groups and Comparisons for Each Study Period and Analysis Population

Study Period	Analysis	Treatment Group	Abbreviation	Inferential
	Population			Comparison
Double-blind, placebo- controlled treatment period (Period 2)	mITT Population Safety Population	Placebo SC Q4W ^a Peresolimab 100 mg SC Q4W Peresolimab 400 mg SC Q4W Peresolimab 1000 mg SC Q4W	PBO PER100Q4W PER400Q4W PER1000Q4W	PER100Q4W vs. PBO PER400Q4W vs. PBO PER1000Q4W vs. PBO
Double-blind treatment period Weeks 12 to 24 (Period 3A)	Maintenance Population	Placebo SC Q4W to Peresolimab 400 mg SC Q4W Placebo SC Q4W to Peresolimab 1000 mg SC Q4W Peresolimab 100 mg SC Q4W Peresolimab 400 mg SC Q4W Peresolimab 1000 mg SC Q4W	PBO/PER400Q4W PBO/PER1000Q4W PER100Q4W PER400Q4W PER1000Q4W	No Between-Treatment Comparison
Double-blind treatment period Weeks 24 to 60 (Period 3B)	Maintenance Primary Population	Peresolimab 400 mg SC Q4W Peresolimab 400 mg SC Q12W Peresolimab 1000 mg SC Q4W Peresolimab 1000 mg SC Q12W	PER400Q4W PER400Q12W PER1000Q4W PER1000Q12W	No Between-Treatment Comparison
	Maintenance Secondary Population	Peresolimab 400 mg SC Q4W Peresolimab 1000 mg SC Q4W	PER400Q4W PER1000Q4W	No Between-Treatment Comparison
	Maintenance Tertiary Population	Placebo SC Q4W to Peresolimab 400 mg SC Q4W Placebo SC Q4W to Peresolimab 1000 mg SC Q4W Peresolimab 100 mg SC Q4W	PBO/PER400Q4W PBO/PER1000Q4W PER100Q4W	No Between-Treatment Comparison
Combined Periods 2 and 3A (Weeks 0 to 24)	mITT Population	Placebo SC Q4W to Peresolimab 400 mg SC Q4W Placebo SC Q4W to Peresolimab 1000 mg SC Q4W Peresolimab 100 mg SC Q4W Peresolimab 400 mg SC Q4W Peresolimab 400 mg SC Q4W Peresolimab 1000 mg SC Q4W	PBO/PER400Q4W PBO/PER1000Q4W PER100Q4W PER400Q4W PER1000Q4W	No Between-Treatment Comparison
Treatment Period (combined Periods 2 and 3; Weeks 0 to 60)	Safety Population (for exposure table)	Peresolimab 100 mg SC Q4W Peresolimab 400 mg SC Q4W Peresolimab 1000 mg SC Q4W	PER100Q4W PER400Q4W PER1000Q4W PER400Q4W/Q12W	No Between-Treatment Comparison

Study Period	Analysis	Treatment Group	Abbreviation	Inferential
	Population			Comparison
	Safety	Peresolimab 400 mg SC Q4W to Peresolimab 400 mg SC	PER1000Q4W/Q12W	

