4.4.2.1.2. DAS28-hsCRP

The change from baseline of DAS28-hsCRP at Week 12 for the peresolimab treatment group will be compared with placebo.

An MMRM model, as described in Section 4.1, will be used to test the treatment difference of each peresolimab treatment group versus placebo. A hypothetical strategy will be used to handle intercurrent events. Any missing data (for example, missing due to missing a visit) will not be imputed.

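### The MMRM fits one baseline slope to all Period 2 visits; if that slope drifts, the secondary Week 12 contrasts may lose some precision that a baseline-by-visit term would recover almost free

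*SAP*

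**What the plan says.** SAP 4.1 assigns the MMRM to "Continuous efficacy endpoints, which are planned to be collected at >1 postbaseline timepoints during Period 2 according to the SoA". Its fixed effects are "treatment, stratification factors, baseline value, visit and treatment-by-visit interaction in the model as fixed factors, and" the list closes with "participant as a random factor". On the covariance it says: "The covariance structure to model the within-participant errors will be unstructured". If that fails to converge, the first fall-back is heterogeneous Toeplitz. Protocol 9.3.1 has the same model; its list ends "visit, and treatment-by-visit interaction in the model as fixed factors, and" the same participant term. Neither document shows a baseline-by-visit term.

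SAP 4.4.2.1 applies this model at Week 12 to DAS28-hsCRP, SDAI, CDAI, the ACR core set, morning stiffness and FACIT-F. For DAS28-hsCRP: "An MMRM model, as described in Section 4.1, will be used to test the treatment difference of each peresolimab treatment group versus placebo". ICEs follow a hypothetical strategy (SAP 1.1): data after rescue, prohibited medication or discontinuation are dropped, and remaining gaps are not imputed. Protocol 9.3.1 assumes missing at random. On reporting and error control: "The 95% CI will also be reported" and "Adjustment for multiple comparisons will not be employed in the analysis for this study".

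**The concern.** Treatment may differ by visit in this model, but the baseline adjustment may not. In repeated measures the link between baseline and the current value often weakens with time. A common slope is then a compromise across visits and need not suit Week 12, the only secondary time point in Period 2. Baseline variation left unexplained at Week 12 goes into the residual variance, and each dose-placebo interval for these endpoints may widen.

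The exclusion of post-event data adds a second route. Where Week 12 values are missing, the model supplies the information from earlier visits. A mean model that is wrong in baseline can then shift the estimate if missingness depends on response.

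**Working it through.** **Inputs from the documents.** Week 12 arm sizes in SAP 5: 60 (100 mg), 120 (400 mg), 120 (1000 mg) and 120 (placebo). Visit 2 is Week 0 (SAP 4.1) and Visit 9 is Week 24 (SAP 1.2). The visit schedule itself is not visible; from the numbering I infer 3 or 4 post-baseline visits by Week 12.

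**The plan's own figure.** 60 + 120 + 120 + 120 = 420, as stated. Nothing else can be reproduced, because no SD, baseline correlation or power is visible for any MMRM endpoint. All covariance inputs below are assumptions.

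**Formula (large sample, complete data).** Let β be the vector of true baseline slopes by visit, R the residual covariance, V the baseline variance and β_c the common slope.

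- β_c = (1'Ω⁻¹β)/(1'Ω⁻¹1), with Ω = R + (β − β_c)(β − β_c)'V
- Week 12 SE ratio, common slope to visit-specific slope = √[1 + (β₁₂ − β_c)²V/R₁₂]

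**A case that can be checked by hand.** Take V = 1, residual SD 1 at every visit and one common residual correlation. All visits then get equal weight, and β_c is the plain mean of the slopes. With slopes falling evenly over 4 visits:

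- 0.50 to 0.50: β_c = 0.50; ratio 1; no loss.
- 0.60 to 0.50: β_c = 0.55; √(1 + 0.05²) = 1.001; SE +0.1%.
- 0.70 to 0.50: β_c = 0.60; √(1 + 0.10²) = 1.005; SE +0.5%.
- 0.85 to 0.50: β_c = 0.675; √(1 + 0.175²) = 1.015; SE +1.5%.

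**Other covariance patterns.** In the first two rows the residual SD rises evenly from 0.6 to 1 with correlation 0.6. In the others the total SD is constant at 1 and correlation decays exponentially, with or without measurement error.

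| Assumption | Slopes, first visit to Week 12 | β_c | First-visit weight | Week 12 SE |
|---|---|---|---|---|
| Rising SD, 4 visits | 0.70 to 0.50 | 0.694 | 0.77 | +1.9% |
| Rising SD, 4 visits | 0.85 to 0.50 | 0.839 | 0.77 | +5.6% |
| Decay with measurement error, Weeks 4, 8, 12 | 0.58 to 0.40 | 0.504 | 0.45 | +0.6% |
| Pure decay, Weeks 4, 8, 12 | 0.67 to 0.30 | 0.549 | 0.64 | +3.4% |
| Pure decay, Weeks 2, 4, 8, 12 | 0.89 to 0.50 | 0.841 | 0.85 | +7.5% |

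For the fourth row: (0.30 − 0.549)² / 0.91 = 0.068, and √1.068 = 1.034. Sharper assumptions go further: 8.5% with a Week 2 visit and a Week 12 correlation of 0.3, and 10.8-14% with pure decay and a Week 1 visit. I treat these as stress cases.

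**Simulation, complete data** (8,000 trials per scenario, arms 120/60/120/120, 4 visits). The SE ratio was 0.999 with equal slopes and 1.022 with slopes falling from 0.80 to 0.52. Bias was within 0.003 and coverage 94.6-95.1% for both models.

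**Simulation, response-related missingness** (120 per arm, 4 visits, correlation 0.6, true effect −0.40; missingness driven by the last observed value and more frequent on placebo; 500 trials each).

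- About 25% missing, slopes 0.88 to 0.47: bias −0.046 (common slope) against −0.003 (by visit), a difference of −0.043. Monte Carlo error is about 0.007.
- About 25% missing, slopes 0.70 to 0.50: −0.026 against −0.007, a difference of −0.019.
- About 10% missing: differences of −0.016 and −0.009.
- Constant slope: no difference.

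The shifts exaggerate the effect.

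**Meaning for power.** For a contrast with 80% power under the by-visit model, at two-sided 0.05 (my assumption), power under the common slope is Φ(2.802/ratio − 1.960). That gives 78.8% at SE +1.5%, 78.4% at +2% and 73.7% at +8%.

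**The case against.** The strongest reply is that this is a prespecified and valid analysis of secondary endpoints, and that nothing in the documents shows the baseline slope drifting. With equal slopes nothing is lost. That stands, and it makes the point conditional.

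Four stronger readings are tempting and are not supported:

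- **Every Week 12 interval is wider than it need be.** This requires drift in each endpoint, which the documents do not show.
- **Week 12 is adjusted with an early-visit slope.** The common slope is weighted by the covariance. Early visits dominate under fast decay or rising variance, but all visits count equally under constant variance and a common correlation.
- **The loss equals about 10 of 120 participants per arm.** That corresponds to 8.6-9.7% in variance, from assumed slopes of 0.85-0.90 falling to 0.45-0.50 over four visits. On the interval scale it is only about 4-5%, and it depends on residual SDs that the documents do not give.
- **The participant random factor will break convergence and trigger the fall-back structure.** Read literally, a random intercept on top of an unstructured matrix is not separately identifiable. But the phrase can simply name the repeated-measures subject, and no calculation tests the convergence claim. It is a wording matter.

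Timing and documentation also count. SAP 4.9 declares no change from the protocol, and the version history places Version 2 before the primary outcome lock and Version 3 only before the final lock. This calls for an open record of the change; it does not remove the gain. Finally, protocol 7.2 expects discontinuation to be uncommon, which keeps any bias small.

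**Conclusion.** The concern holds in a limited, conditional form. Both documents fit one baseline slope across Period 2. If the slope declines over visits, the secondary continuous Week 12 contrasts may lose precision: nothing with equal slopes, about 0.1-2% of the SE with a mild decline, about 1.5-8% with a steep one. These ranges rest on assumed slopes, correlations, residual SDs and 3 or 4 visits.

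A reader might infer that the planned tests are biased or invalid. With complete data they are not, because the unstructured variance absorbs the misfit. With response-related missingness a bias of about 0.02-0.04 SD units is possible at roughly 25% missing, and less at 10%. The primary ACR20 analysis (logistic regression with nonresponder imputation) and the SF-36 ANCOVA do not use this model. This is a worthwhile small improvement; it does not threaten the trial's main conclusion.

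**What to change.** Add a baseline-by-visit interaction to the MMRM fixed effects in SAP 4.1. It costs the number of visits minus 1, so 2-3 parameters in about 420 participants; if the slopes are in fact equal, the SE is at most about 0.1% larger.

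Record the addition, with its reason, in SAP 4.9 and the clinical study report as a change from the protocol 9.3.1 model. Protocol 9.3.1 requires this for analysis changes that do not need an amendment. If Week 12 results are already unblinded, show the prespecified model beside the extended one.

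As a clarification only, replace the random-factor line with a statement that participant is the repeated-measures subject for the unstructured covariance and that no separate random intercept is fitted.
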